Hypothesis: All three non-surgical UI management options for women are feasible (as measured by 80% adherence to treatment assignment over 7 days) and tolerable (as measured by patient report via questionnaire).

The results from our proposed aims will provide important information about the experiences and symptom burden of women with CF and UI. Importantly, we will also be able to answer the important questions of "Can it work?" and "Does it work?"¹⁵ as we seek to construct the definitive, adequately powered trial of these therapies in women with CF and UI.

B. INNOVATION STATEMENT:

This proposal is the first formative research exploring the mechanism of UI in women with CF and patient experiences and perceptions regarding UI and their treatment options. It will also be the first to assess feasibility and symptom improvement of nonsurgical treatment modalities for this population. As such, these are all important steps to 1) learn where to focus patient and provider education efforts and changes to the CF care model, 2) begin to understand what treatment may be preferred by and feasible for women with CF, and 3) clarify the underlying cause of UI. Results will inform the content and design of a future multi-center, randomized trial aimed at determining the best option for nonsurgical treatment of UI (PFMT with bladder training, urethral support devices, or reusable absorbent products) in women with CF. Importantly, subjective and objective data will provide key data points to allow for power calculations of this trial and multiple patient feedback assessments will be utilized to determine feasibility of future trial. Utilization of patient consultants will provide additional input to ensure successful completion of aims and design of future trial. Given that a robust feasibility trial ensures a realistic assessment and capability to conduct the clinical trial¹⁶, we feel this proposal has the chance to innovate care of women with CF and UI.

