diary for a total of 7 days. Reusable absorbent pad cohort – Two pairs of Speax underwear will be provided and subjects will complete a similar daily UI diary for 7 days. PFMT cohort - Experienced pelvic health physical therapists (at both University of Pittsburgh and at Johns Hopkins University) will complete two visits one week apart. We will develop a standardized pelvic floor exercise intervention based on previous RCT for PFMT in women with MUI.⁴⁴ The intervention will comprise: 1) Bladder training and delayed voiding techniques 2) Urgency suppression 3) SUI strategies (e.g., 'knack') and 4) PFM training for those agreeable to internal exams.⁴⁵ We were aware of the potential challenges for standardization of this type of intervention and ensuring consistency across multiple sites. We will limit the involvement to one experienced PT at each site and create a standardized protocol guided by both patient consultants, previous evidence, and expertise of [name], RT. Subjects will not be blinded to their group assignment given the nature of the differences in management options. At the end of the treatment assignment all subjects will repeat the KHQ and a patient global impression of improvement (PGI-I). The PGI-I is a validated one question measure rating their urinary tract condition now, as compared with how it was prior to before beginning treatment on a scale from 1 (Very much better) to 7 (Very much worse).⁴⁶

Given the opportunity to gather acceptability on these options for a sensitive issue, subjects will be offered an option to further participate in one alternate therapy of their choosing. If they select this option we will organize an additional week of therapy and have them complete another PGI-I at the end of therapy.

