Acceptability and Feasibility assessment: Urethral support device cohort and Reusable absorbent pad cohort: Feasibility will be evaluated through assessment of use and product performance. Logs regarding utilization of assigned product will be completed daily. Patient treatment preference will be assessed after completion of both therapies utilizing the product performance questionnaire (PPQ).⁴⁷ The PPQ is a 17-item product questionnaire that consists of product questions that are specific to incontinence products and includes questions about overall impression of product, ability to hold urine, ability to prevent odor, fit, discreteness, comfort when wet and dry, and ability to keep skin dry.⁴⁷ PFMT cohort: Feasibility will be evaluated through assessment of adherence and self-reported success with ability to perform exercises. Adherence to intervention sessions will be documented by physical therapist using attendance logs. Adherence to home practice will be documented by participants in home logs that included the dates and times of practice. At the end of each physical therapy visit, participants will be asked to rate their confidence in performing the PFMT exercises featured in their program (extremely, very, moderately, somewhat, and not at all confident).

At the end of the cohort, all participants will be asked to indicate how easy it would be to continue practicing their assignment intervention (extremely, very, moderately, somewhat, and not at all easy).⁴⁸ All subjects will complete a Benefit, Satisfaction, and Willingness to Continue (BSW) questionnaire.⁴⁹ We will consider therapy feasible (as measured by 80% adherence to treatment assignment over 7 days) and tolerable (as measured by patient report via questionnaire). By allowing subjects to choose another one of the arms after their randomization this will give us further, important information about feasibility and patient preference for a larger trial.

Table 2: Study Flow

	Pre-baseline visit	Baseline Visit (in-person)	Randomized Trial Period							One week Cross-Over Period (optional)	End of Study
			D1	D2	D3	D4	D5	D6	D7		
Informed Consent	x	x									
KHQ		x									
Bladder diary	x		x	x	x	x	x	x	x		
Cough Stress test	x										
Randomization	x										
PGI-I									x		x
BSW								x			x
Cohort Specific Measures											
Urethral support device Cohort										x	
Reusable Underwear Cohort										x	
Utilization log			x	x	x	x	x	x	x		
PPQ			x	x	x	x	x	x	x		

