Physical Therapy Cohort											
Physical Therapy Visit			x						x		

Attendance Log			x				x		
Confidence scale			x				x		

KHQ, King's Health Questionnaire; PGI-I, Patient Global Impression Improvement – Incontinence; PFMT, pelvic floor muscle therapy; PPQ, product performance questionnaire; BSW, Benefit, Satisfaction, and Willingness to Continue questionnaire

Data analysis: Descriptive statistics will summarize feasibility survey measures and use log data with sample means and standard deviations calculated for continuous variables and sample proportions for categorical variables with 95% confidence intervals. Due to the pilot nature of this trial, our analytic strategy centers on calculation of point estimates and 95% confidence intervals of our feasibility measures as primary outcomes, rather than hypothesis testing. We will compare initial subjective scores of UI to objective measures utilizing correlation coefficients. To explore preliminary efficacy, PGI-I score will be compared between groups utilizing ANOVA and post-hoc testing. Paired t-test will be used to examine if there is statistically significant difference in the average KHQ scores between arms. The mean PPQ scores will be compared between the Impressa® urethral support and Speax™ underwear and mean BSW score will be compared between all groups. For our randomized trial, we will recruit a total of 30 patients in order to have 80% power to detect at least a 10 point difference in total KHQ score with a significance level of 0.05 and assuming upwards of a 20% attrition rate for the study. Again, the feasibility trial is primarily designed to provide data to utilize for power calculations in future study designs.

F. Limitations and Potential Pitfalls:

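### Does the 80% adherence criterion need a stated unit, and a named PFMT record, before it can serve as the feasibility outcome?

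*Combined protocol and SAP*

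**What the plan says.** One criterion covers all three therapies. The Aim 2 hypothesis in section A reads "All three non-surgical UI management options for women are feasible (as measured by 80% adherence to treatment assignment over 7 days"), and section E, Aim 2, Acceptability and Feasibility assessment, repeats it: "We will consider therapy feasible (as measured by 80% adherence to treatment assignment over 7 days").

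The records behind the criterion differ by arm.

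- Device and underwear: "Logs regarding utilization of assigned product will be completed daily".
- PFMT visits: "Adherence to intervention sessions will be documented by physical therapist using attendance logs". The Aim 2 study procedures say that the therapists "will complete two visits one week apart".
- PFMT home practice: "Adherence to home practice will be documented by participants in home logs that included the dates and times of practice".

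The Aim 2 Data analysis paragraph plans to summarise "use log data with sample means and standard deviations calculated for continuous variables and sample proportions for categorical variables", each with a 95% interval. It describes the strategy as "point estimates and 95% confidence intervals of our feasibility measures as primary outcomes" and sets this against hypothesis testing. It does not say whether adherence is treated as a continuous or a categorical variable.

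**The concern.** Feasibility is the primary outcome of Aim 2, and the plan turns it into a yes-or-no statement for each therapy. A percentage with no stated numerator can be computed in at least two ways: pool all days or visits in the arm, or classify each woman and count those who adhere. The Data analysis paragraph allows either. If the choice were made after the logs had been read, it could decide whether an arm is called feasible, even with no woman lost and no log missing.

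PFMT raises a further difficulty. With two visits, a woman's attendance can only be 0%, 50% or 100%, so one missed visit puts her below 80%. A product user who misses one day is at 6/7 = 86% and stays above it. Section A expects that adherence to PFMT may be lower than to the products, and a coarser scale could produce the same appearance. The plan also does not say how unreturned logs or women who stop early are counted.

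**Working it through.** The 80% is a chosen criterion, so there is no derivation to reproduce. The check is whether reasonable readings disagree, how often, and what depends on it.

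**Inputs from the plan.** 30 women allocated 1:1:1, so 10 per arm; two PFMT visits; seven product days; an 80% cut.

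**Assumptions.** Under the share-of-women reading, a woman adheres if she herself reaches 80%, and the therapy is feasible if at least 8 of 10 women adhere. The plan does not give that second cut. All adherence rates below are illustrative.

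**Worked cases, complete data.**

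| Arm | Pattern | Pooled | Share of women |
|---|---|---|---|
| PFMT visits | 7 attend both, 3 attend one | (14 + 3)/20 = 85% | 7/10 = 70% |
| PFMT visits | 6 attend both, 4 attend one | (12 + 4)/20 = 80% | 6/10 = 60% |
| Product days | 6 women on 7 days, 4 on 5 days | (42 + 20)/70 = 89% | 6/10 = 60% |
| Product days | 8 women on 6 days, 2 on 3 days | (48 + 6)/70 = 77% | 8/10 = 80% |

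For visits, the pooled figure can never be below the share attending both, so any conflict runs one way. For days it can run either way.

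**Frequency, PFMT visits.** Suppose all attend visit 1 and the number attending visit 2 is Y ~ Bin(10, v). Pooled visits pass if 10 + Y ≥ 16, that is Y ≥ 6. The share of women passes if Y ≥ 8. The verdicts differ when Y is 6 or 7. With a cut of 7 women in 10 instead, they differ only when Y = 6.

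| v | 0.6 | 0.7 | 0.8 | 0.9 |
|---|---|---|---|---|
| Cut of 8 in 10 | 47% | 47% | 29% | 7% |
| Cut of 7 in 10 | 25% | 20% | 9% | 1% |

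The frequency therefore depends heavily on a cut that has to be supplied from outside the plan.

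**Frequency, product days.** With beta-binomial days and within-woman correlation from 0 to 0.8, the readings differ in 8–44% of arms at mean daily use 0.80, 3–23% at 0.90 and 1–5% at 0.95.

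**Missing logs.** Under the share-of-women reading, at least two women must be lost before the denominator can change the verdict. Under pooled days, one is enough. All randomised women need 0.8 × 70 = 56 days. Logs returned by nine women need 0.8 × 63 = 50.4, so 51 days. Totals of 51 to 55 split the verdict. With one woman lost and independent days, X ~ Bin(63, p) gives P(51 ≤ X ≤ 55) = 45% at p = 0.80 and 28% at p = 0.90.

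**What the label can carry.** Exact 95% intervals are 35% to 93% for 7/10 women and 44% to 97% for 8/10. One result falls below the cut and the other meets it, yet the intervals almost coincide.

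**What depends on it.** The Data analysis paragraph makes estimates and intervals primary. No progression or stopping action is attached to 80%. Between-group comparisons are planned for PGI-I, KHQ, PPQ and BSW, but not for adherence. Section H schedules finalising the Aim 2 protocol with Aim 1 data.

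**The case for a change.** The best argument for a change is that this is a primary outcome, that readings disagree most when true adherence is near the sponsor's own threshold, and that naming the quantity costs a sentence. An interval also needs a defined quantity, so reporting estimates instead of tests does not remove the question. Fixing the unit before data are seen prevents choosing it afterwards.

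Most of that stands as description. The criterion is incomplete, and nothing else in the document completes it. The seven-day period together with daily logs points to days for the two products, but it does not settle averaging against counting women, and it does not fit two PFMT visits.

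It does not follow that the plan must change. Nothing stated is wrong: a mean share of days and a share of adherent women are both ordinary feasibility summaries, and the same logs yield both. The comparison between arms is an informal expectation with no planned test, so a coarser PFMT scale affects interpretation only. Pooling visits need not penalise PFMT either: if all women attend visit 1, the arm cannot fall below 50%.

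More specific remedies bring their own debatable choices. A per-woman rule still needs a day threshold and a required share of women. Scoring PFMT on home practice alone would take therapist-recorded attendance out of the verdict, although the plan names attendance as adherence to sessions. It would also need a practice schedule, and the standardised exercise protocol is still to be written. Counting every blank day as non-use is conservative but is not the only reasonable rule. The apparent lack of a home-log row in Table 2 carries no weight, because the table is broken in extraction and the text already plans the log.

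**Conclusion.** No change follows. The 80% criterion leaves open what is counted, which PFMT record it uses and who is in the denominator. With complete data from 10 women per arm, the two natural readings can disagree: in 47% of arms at 0.6 or 0.7 attendance of visit 2, 29% at 0.8 and 7% at 0.9. These figures assume that all women attend visit 1 and that 8 of 10 women is the required share; with 7 of 10 they fall to 25%, 20%, 9% and 1%.

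This is missing detail in a 30-woman pilot whose primary output is estimates with intervals, and no decision is tied to the cut. Analysts can fill it sensibly at the planned finalisation of the Aim 2 protocol by naming one summary and denominator, showing the other summary beside it, and keeping attendance and home practice visible separately. Readers would then have what they need to plan the larger trial, whichever summary carries the feasibility label.

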Data Analysis: Transcripts will be analyzed through an iterative process of coding to identify themes. The principal investigator (PI) will develop an initial set of codes. Two coders will then independently review each transcript to apply the initial codebook and to identify additional codes using the NVivo qualitative analysis program. Using a consensus coding approach, after the first few transcripts are independently coded, the coders will meet to review their coding, discuss any discrepancies, and define any new codes; this will be repeated with subsequent transcripts using an iterative process until no new codes emerge. A senior co-investigator will be available to adjudicate any differences in interpretation and review the codebooks. The final coding scheme will be applied to all transcripts and the investigative team will identify central themes on the UI patient experience and treatment knowledge and preferences of women with CF. Representative quotations will be selected to illustrate themes identified.

[figure not shown]
Aim 2. – Evaluate the feasibility of a randomized controlled trial of non-surgical UI management options for women with CF.

Overview: Nonsurgical therapies for UI include 1) behavioral training (e.g., bladder training, to teach one to gradually hold urine for longer periods), 2) PFMT to improve function of the pelvic musculature, and 3) urethral support devices.³⁸ Additionally, newer reusable absorbent underwear have been used to decrease common issues with disposable pads such as vulvar irritation.¹² To inform a larger trial, we propose a randomized, feasibility trial of a disposable urethral support device (Impressa®), Speax™ Reusable Underwear, or PFMT. As there is no current data on objective physical exam findings in women with CF and UI and, thus, limited evidence supporting the belief that this is SUI, all subjects will have a non-invasive pelvic exam to complete a non-instrumented cough stress test (CST) with a full bladder.³⁹ Together, data on objective findings, baseline subjective bother on validated questionnaires, and improvement of symptoms will aid in power calculations for future, multi-center trial for treatment options in women with CF and UI.

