Description of Participants and Participating Study Sites: *Inclusion criteria:* 1) Female age 18 years or older 2) Diagnosis of CF 3) Self-reported UI (at least answer of “a little” on King’s Health Questionnaire – Question #2) 4) Fluent in spoken English 5) Ability to present for in-office exam and study procedures

Recruitment sites: Cystic Fibrosis Center (CF Center) at the University of Pittsburgh and the Johns Hopkins Cystic Fibrosis Center. These two sites have a current working relationship and also the capabilities for study procedures as discussed in facilities section. **Study Procedures:** Participants will be recruited at routine CF clinic visits and via telephone screening. Informed consent will be obtained before any study procedures are initiated. **Baseline visit.** Initial demographic questions and the King’s Health Questionnaire⁴⁰ will be completed at the baseline visit. Subjects will be given materials to complete a 2-day bladder diary.⁴¹ Participants will then have a pelvic exam for a visual urethral mobility examination⁴² and assessment of pelvic floor muscle strength.⁴³ This exam will be completed by the urogynecology faculty at either site. We will first perform a bladder scan ultrasound to assess current bladder volume and then a cough stress test (CST). (Figure 1) The exam will be performed in the supine/lithotomy position with ≥ 300 mL of fluid in the bladder. We will have the subject cough forcefully 1-4 times and the examiner will directly visualize the urethral meatus for the presence of leakage. Leakage of fluid from the urethral meatus coincident with/simultaneous to the cough(s) is considered a positive test consistent with SUI.

FIGURE 1

Randomized feasibility trial (Table 2). At the baseline visit, women will be randomized to either a disposable urethral support device (Impressa®), Speax™ Reusable Underwear, or PFMT. Randomization will be in a 1:1:1 allocation stratified by site. The disposable Impressa® urethral support is a tampon-like device that is available over the counter to help women with UI. Speax Reusable Underwear are similarly available for purchase online and are absorbent underwear for bladder leak protection. **Urethral support device cohort** - A week supply of the Impressa device will be provided and participants will be asked to complete a daily bladder

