Strengths of our study include the ability to quickly complete Aim 1 to allow for adequate time to complete Aim 2. The main limitation of our study is the small sample size in Aim 2, but given the primary goal of assessing feasibility, these aims primarily serve to inform our larger trial design. Additionally, in view of the lack of available data, these will be important stepping stones to adequately power future studies. Although the lack of a control group could be seen as a limitation, there is such a vast body of literature surrounding prevalence and quality of life in pre-menopausal women with UI.⁵⁰ Recruitment and retention of subjects can always pose a challenge. We will leverage the strong background of recruitment at our sites and the experience of our research coordinators to ensure adequate completion of aims. For Aim 1, we have a plan to recruit from Community Voice for aim 1 but can also recruit directly from participating centers. We have already communicated with Community Voice and have a letter of support included in our application. For Aim 2, we will start our feasibility trial by the end of year one of the grant period, so we are confident in our ability to complete our proposed aims in the study period. Additionally, the co-investigators Drs. [name] and [name] are well-connected in the CF community and members of the CFF Women's Health Research Working Group. Thus, we foresee minimal issues forming additional partnerships with another CF center (such as University of Texas-Southwestern, University of Washington, or National Jewish), if necessary.

G. Consultant Arrangements: [name] and [name], both women with CF who have sought care for their experience with UI, will serve as consultants on this grant. They will assist in study design, interview guide development, data analysis, and the writing and preparation of all manuscripts resulting from this research. In particular, they will provide a patient perspective, which is vital to this project. A Letter of Support is attached.

H. TIMELINE

	Year 1					Year 2			
	Pre-award	Q1	Q2	Q3	Q4	Q1	Q2	Q3	Q4
IRB application and approval aim 1									
Protocol final aim 1									
Aim 1 “Qualitative Interviews”		Recruit Participants			Transcription and Data Analysis				
		Complete Interviews							
Aim 2 “Randomized Feasibility Trial”			Finalize protocol using data from Aim 1						
					Recruit Participants				
					Begin and Execute Trial			Complete Trial	
									Data analysis

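### Randomisation is stratified by site, but the exploratory PGI-I ANOVA names no site term and loses precision if sites differ by an amount common to the arms

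*Combined protocol and SAP*

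**What the plan says.** Section E, Aim 2, names two recruiting centres: "Cystic Fibrosis Center (CF Center) at the University of Pittsburgh and the Johns Hopkins Cystic Fibrosis Center". Under the randomized feasibility trial it states "Randomization will be in a 1:1:1 allocation stratified by site". It does not say how arms are kept in balance within a site (block size or other method).

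The Aim 2 Data analysis paragraph is the only analysis text for the trial. For PGI-I it says "PGI-I score will be compared between groups utilizing ANOVA and post-hoc testing". KHQ gets a paired t-test, and PPQ (two products) and BSW (all groups) have their means compared by an unnamed method. Site is not mentioned as a factor, stratum or covariate in any of these.

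The same paragraph makes the primary results point estimates and "95% confidence intervals of our feasibility measures as primary outcomes, rather than hypothesis testing", and presents the PGI-I comparison as exploratory. It adds that "the feasibility trial is primarily designed to provide data to utilize for power calculations in future study designs". The Aim 2 Overview says that "improvement of symptoms will aid in power calculations for future, multi-center trial". Section F allows for recruiting a further CF center if needed.

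**The concern.** Stratifying by site makes site part of the design. An ANOVA on arm alone then ignores it. If patients at one site give systematically better or worse PGI-I ratings, by the same amount in every arm, that difference is explainable variance which the arm-only model leaves in its error term.

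What follows depends on the allocation method:

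- **Arms balanced within site.** The estimated arm difference is the same with or without site, but its standard error is overstated, the interval is too wide and the test rejects too seldom.
- **Arms not balanced within site.** Chance imbalance in site mix adds noise to the arm difference itself, while the test stays near its nominal level.

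At stake is the precision of one exploratory comparison in a trial of 30, whose symptom data are meant to inform planning of a larger one.

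**Working it through.** **Inputs from the plan.** Total N is 30 in three arms, with up to 20% attrition: 30 × 0.8 = 24 completers, 8 per arm. Two sites. PGI-I runs from 1 to 7.

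**The plan's own figure.** The 30 is justified by 80% power for a 10-point KHQ difference. No SD is given, so it can be neither reproduced nor refuted. With 8 per arm and a normal approximation it would need an SD of about 7.1. It concerns KHQ, and nothing below depends on it.

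**Assumptions.** The documents give neither a PGI-I SD nor a site difference. I take within-site SD = 1 and a site difference d of 0, 0.5 or 1, common to all arms, with 15 patients per site.

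**Step 1: exact balance (4 per arm per site), closed form.** Arm-only residual variance = 1 + N·d² / [4(N − 3)], with N = 24:

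- d = 0.5: 1 + 24 × 0.25 / 84 = 1.071, so the SD is 3.5% too large.
- d = 1: 1 + 24 / 84 = 1.286, so the SD is 13.4% too large.

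Adding site takes the error df from 21 to 20. At d = 0 this costs t(20)/t(21) = 2.086/2.080 = 1.003, about 0.3% in width.

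**Step 2: other allocation methods, by simulation.** 40,000 trials per setting, normal outcome; outside the exact-balance row, 24 of 30 are kept at random. Entries are for d = 0, 0.5, 1.

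| Allocation within site | Type I error, arm-only | Change in CI width from adding site |
|---|---|---|
| Exact balance | 5.0%, 4.4%, 2.3% | +0.3%, −3.2%, −11.6% |
| Blocks of 3 | 5.0%, 4.3%, 2.9% | +0.7%, −2.6%, −10.9% |
| Blocks of 6 | 5.1%, 4.6%, 3.1% | +1.0%, −2.3%, −10.6% |
| Simple | 4.8%, 4.9%, 5.1% | +2.8%, −0.4%, −8.4% |

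With site in the model, type I error is 4.8% to 5.2% throughout. Adding site breaks even near d = 0.25 with blocks of 3 and near d = 0.5 with simple allocation.

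**Step 3: the two mechanisms.**

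- Exact balance, assumed gap of 1.5 SD between the extreme arms with the third midway: arm-only power is 67.2% at d = 0.5 and 58.2% at d = 1, against about 70% with site.
- No within-site balance, d = 1: the SD of the estimated arm difference is 0.55 without site and 0.51 with it, and type I error is about 5% either way.

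**Step 4: sensitivity.**

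- PGI-I rounded to 7 points, within-site SD about 1.2 points, shifts of 0, 0.6 and 1.2 points: +0.7%, −2.4%, −10.4% (blocks of 3); +2.8%, −0.2%, −8.0% (simple).
- Sites split 21:9: +0.8%, −2.1%, −9.3% (blocks of 3); +2.8%, +0.1%, −6.9% (simple).
- Three equal sites with shifts 0, d/2, d: at d = 0, +1.9% (blocks of 3) and +5.8% (simple); at d = 0.5, −0.1% and +3.6%.

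**The case against.** The strongest reply is that nothing in the documents shows a site difference common to the arms. PGI-I asks each woman to rate her condition against how it was before treatment, so a difference between sites in baseline severity need not carry over. Below about 0.25 to 0.5 SD the site term is neutral or slightly harmful, and a clear gain needs something near 1 SD. The comparison is exploratory, the text is brief, and the word ANOVA does not exclude a second factor. All of this stands, except that arm-only is the natural reading of the sentence. It limits the severity; it does not remove the mismatch between design and analysis.

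Three stronger readings may tempt a reader, and the documents do not support them:

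- **That the arm-only test is invalid or biased.** It is not: type I error is at or below about 5% in every setting above.
- **That the one-therapist-per-site arrangement shows that sites will differ.** The plan does mention "potential challenges for standardization of this type of intervention and ensuring consistency across multiple sites", but that remark concerns PFMT only. A PFMT-only difference is not common to the arms, and a site main effect hardly absorbs it. At 1 SD with exact balance the residual variance is 1 + 2/21 = 1.095 for arm-only and 1 + 1.333/20 = 1.067 with site, so 0.067/0.095, about 70% of the excess, remains.
- **That every between-arm comparison needs a site term.** The paired t-test named for KHQ has no place for one, and in within-person change a stable site difference in level cancels. The two-arm PPQ comparison can lose precision: with site added, its interval is 1.5% (blocks of 3) to 4.9% (simple) wider if sites do not differ.

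**Conclusion.** The point holds for the PGI-I ANOVA and is minor. The plan stratifies by site and names no site term in that analysis. If sites differ by an amount common to the arms, precision is lost. The amount cannot be determined from the documents: it is nothing at d = 0, slight at 0.5 SD, and about 8% to 11% of interval width at 1 SD with two sites and 24 completers. These figures rest on the assumed shifts and, between blocked and simple allocation, on a method that the plan does not state.

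A reader might also infer that the future trial will be planned on too large an SD. That does not follow. The plan does not say which SD will be carried forward or what model that trial will use; for an unadjusted trial the arm-only SD is the relevant one. The excess, 3% to 13%, is also smaller than the sampling error of an SD on 21 df, whose 95% interval runs from −23% to +43%.

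The primary feasibility estimates and their intervals do not change.

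**What to change.** In the Aim 2 Data analysis paragraph, replace the PGI-I sentence with: *PGI-I will be analysed by ANOVA with arm and site (the randomisation stratum) as fixed factors; post-hoc tests and 95% CIs for arm differences will be taken from that model.* Leave the KHQ and PPQ comparisons out of this change.

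The cost is one sentence and no new data, since site is already recorded. It can be made at the timeline step "Finalize protocol using data from Aim 1". Statistically it costs one degree of freedom per site beyond the first. If sites do not differ, the interval for an arm difference is about 1% (blocked) to 3% (simple allocation) wider with two sites, and about 2% to 6% wider if a third site joins.
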